Preventing Sexual Violence Through a Comprehensive, Peer-led Initiative

NCT03207386

August 19, 2021

Study Protocol

Written parental consent and student assent were required for youth to complete the study, consisting of five survey waves. Any youth in grades 7 to 10 ($n = 4,172$) at the beginning of the Fall 2017 semester were eligible and invited to enroll in the survey; the first survey occurred between October 2017 and December 2017. We used intensive recruitment procedures such that the consent forms were sent to parents in multiple ways (i.e., via their students from school, mailings, email) and we called and conducted home visits to households in which consent forms had not been returned. We also had multiple ways in which the consent forms could be returned (e.g., email, text, in person). At study initiation, of the 4,172 eligible students, the majority ($n = 3,257$; 78.0%) of youth returned the consent forms, and of those that returned the forms the majority ($n = 2,667$; 81.8%) of guardians gave permission for their student to take the survey. Most students ($n = 2,232$; 83.6%) with guardian permission took the survey. Figure 1 depicts eligibility and participation by wave. Past W1, we conducted ongoing study recruitment, such that we mailed consent forms to new students and followed up with calls and home visits, provided consent forms during in-school surveys, and offered consent forms at various community and school events.

The survey was administered on computers in school by trained research staff. All students had unique logins that were created in part so that students only with parental permission could access the survey. Students received a small incentive (e.g., fruit snack, pencil) and were entered to win one of twenty \$100 gift cards which increased by \$50 at each of the four subsequent surveys. Students who completed all surveys were entered into a drawing to receive a large prize equal to \$1,000 (e.g., tablets, pizza party). At each wave, students who missed the in-school survey ($n = 475$ -1,289 across waves), were sent a letter in the mail requesting that they

take the survey online; instructions were provided for how to take the survey online. Return rate of these out-of-school surveys ranged from 1.8% to 8.4%. Overall, retention from W1 ranged from 58.3% to 85.6% across waves. The highly transient nature of the community where data were collected was a large factor in participant attrition; the most common reason for not participating was absence from school, and many of those absences were from students who had left the district. If students who left the district were not considered in retention analysis (e.g., removed from the denominator), retention from W1 ranged from 87.9% to 98.7%. We identified inattentive responders (students taking the survey) using questions like “Do you have more than 10 kids?” By the last wave, 108 participants (4.1%) were identified as an inattentive responder and removed from analyses.

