**Preventing Sexual Violence Through a Comprehensive, Peer-led Initiative**

**NCT03207386**

**August 19, 2021**

## Data Analyses

All analyses were estimated in Stata 15. In all analyses, we used multiple imputation (MI; 20 imputed datasets) to address attrition and other missing data (Lang & Little, 2018). To address *Aim 1a*, we conducted a series of logistic regression analyses, one for each of the dichotomous W3 outcomes (i.e., sexual perpetration, sexual victimization). Covariates were sex (1 = *male*), ethnicity (1 = *Hispanic/Latinx*), race (1 = *White*), sexual orientation (1 = *sexual minority*), age (higher = *older*), school (dummy coded with the largest school as the comparison group), and the W1 outcome score (as applicable to each model).

Data collection protocols allowed for analysis of the long-term impact of the large camp and short-term impact of the small camp. However, because large and small camp attendance (e.g., youth could attend both camps) may co-vary they were included in the same model. That is logistic regression models examined the effects of both large camp attendance (0 = *did not attend*; 1 = *attended*) and small camp attendance (0 = *did not attend*; 1 = *attended*) on each primary outcome included in the model.

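### Does the removal of 108 inattentive responders leave the W3 analysis set open enough to require a change to the plan?

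*Protocol*

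**What the plan says.** The exclusion is in the last two sentences of the Protocol. The method comes first: "We identified inattentive responders (students taking the survey) using questions like", followed by an example of an implausible item. The result comes next: "By the last wave, 108 participants (4.1%) were identified as an inattentive responder and removed from analyses". The Protocol gives no number of failed items needed for a flag and no breakdown of flags by wave or by camp attendance.

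The Protocol also refers to a participation figure, "Figure 1 depicts eligibility and participation by wave", whose content is not in the text available for review. It gives the number of W1 survey takers, "Most students ($n = 2,232$; 83.6%) with guardian permission took the survey", and notes later enrolment: "Past W1, we conducted ongoing study recruitment".

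The SAP (Data Analyses, first paragraph) fits logistic regressions, "one for each of the dichotomous W3 outcomes (i.e., sexual perpetration, sexual victimization", adjusted for the W1 score among other covariates. On missing data it says: "In all analyses, we used multiple imputation (MI; 20 imputed datasets) to address attrition and other missing data". It does not mention inattentive responders.

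**The concern.** The exclusion count runs to the end of the study, but the modelled outcomes are measured at the third of five waves. If a flag at any wave removes a student from every analysis, a student with a usable W3 report could leave the W3 model because of answers given at W4 or W5. Membership of the analysis set would then depend on behaviour after the outcome. That can distort the association between camp attendance and the outcome if late flags are related to both jointly.

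Two further questions follow. If only the flagged survey was discarded, its answers would become missing and could be imputed, which gives a different analysis set from dropping the student. And the percentage has no stated base: 108 out of the 2,232 W1 takers is 4.8%, not 4.1%.

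At stake is whether a reader can reconstruct who is in the perpetration and victimization models. The outcomes are sensitive self-reports, for which careless answers and true reports are hard to tell apart.

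**Working it through.** **Base of the 4.1%.** Inputs, all from the Protocol: 108 removed; 4,172 eligible; 3,257 forms returned; 2,667 guardian permissions; 2,232 W1 takers. Share = 108 / base.

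- 108/4,172 = 2.59%
- 108/3,257 = 3.32%
- 108/2,667 = 4.049%
- 108/2,232 = 4.84%

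No count in the text gives 4.1% at the printed precision. Working backwards, 108/0.041 = 2,634. If 4.1% is rounded (4.05% to below 4.15%), the base is 2,603 to 2,666. If it is truncated (4.1% to below 4.2%), the base is 2,572 to 2,634. Truncation is plausible, because the three neighbouring percentages look truncated:

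- 3,257/4,172 = 78.07%, printed 78.0
- 2,667/3,257 = 81.89%, printed 81.8
- 2,232/2,667 = 83.69%, printed 83.6

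**Is such a base credible?** Only students who took a survey can be flagged, so the natural base is everyone ever surveyed. The excess over the W1 takers is 2,603 − 2,232 = 371 to 2,666 − 2,232 = 434 (rounded), or 2,572 − 2,232 = 340 to 2,634 − 2,232 = 402 (truncated). At study initiation 2,667 − 2,232 = 435 students had permission but did not take W1, and recruitment continued afterwards. Late starters from either source could supply the excess, so the figure is consistent with the rest of the text. It does not show that the additional students were recruited after W1.

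**Person or survey.** The Protocol's sentence has participants as its subject and says that they were removed from analyses. Nothing in the SAP says that flagged answers were set to missing. Whole-person removal is the plain reading.

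**Which waves' flags.** The number removed from the W3 models only because of flags at W4 or W5 is not given. Its limits are 0 and 108, or 0% to 4.1% of the implied base. The upper limit requires that nobody was flagged in the first three waves.

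**Effect on the odds ratio.** Let s(a,y) be the proportion kept among students with attendance a and outcome y. Then, before covariate adjustment,

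OR after removal = OR before × [s(1,1) × s(0,0)] / [s(1,0) × s(0,1)].

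If removal depends on attendance alone, or on the outcome alone, the multiplier is 1. It departs from 1 only if the relation between removal and outcome differs between attenders and non-attenders. The documents give none of the four proportions, so the multiplier cannot be computed.

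**The case for a change.** The strongest opposing case accepts whole-person removal and turns it round. Read literally, a flag at any of five waves removes the student from everything, and that is the one reading under which answers after the outcome decide who is analysed. An example can be built to show that this could matter. Assume no camp effect, a W3 risk of 5% to 10%, an equal removal rate of 108/2,634 = 4.1% in both attendance groups, and removed students who report the outcome 5 times as often as their group among attenders but 2 times among the others. With kept risk = p(1 − kr)/(1 − r), where p is the W3 risk, k the reporting ratio and r the removal rate, the odds ratio after removal is 0.85 to 0.86. Swapping the ratios gives 1.16 to 1.17.

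The arithmetic is right, but it is not evidence about this trial. The 5-versus-2 contrast has no source in the documents and produces the whole shift: with equal ratios the result is 1.00. The example also needs all 108 to have been flagged only after W3, treats 2,634 as the W3 analysis set, and ignores the covariates. Even if its inputs were true, it would measure the distance between two analysis sets and not bias. If the removed students' W3 answers were careless, removing them improves the estimate.

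What stands is narrow. The text does not say whether flags raised after W3 counted for the W3 models, and it does not restate the denominator. One or two sentences would help a reader on both.

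**Conclusion.** No change to the plan follows. The unit removed is stated. The percentage is consistent with a base of about 2,572 to 2,666 students, and the missing denominator has no bearing on any W3 estimate. The remaining gap, the waves whose flags counted, is a detail that analysts can fill sensibly in either of two ways. Excluding anyone ever flagged treats inattention as a mark of an unreliable respondent. Excluding only on flags up to W3 avoids selection on later behaviour but keeps W3 answers from students who were careless later. That is a fair trade-off, and the documents do not show that one choice is wrong.

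On size, between 0 and 108 students (at most 4.1%) could be affected, with no evidence that the number exceeds 0. For scale, 14.4% to 41.7% of W1 participants were not retained at later waves (100 − 85.6 and 100 − 58.3), a far larger source of missing data, which the SAP does address. A W3 sensitivity analysis would have a purpose only if late flags were in fact used, which the documents do not show.

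This conclusion rests on the plain reading of the exclusion sentence, and on not counting as missing what Figure 1 may contain. It would need another look if many first flags arose at W4 or W5 and their relation to the W3 outcomes differed by camp attendance.

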**Preventing Sexual Violence Through a Comprehensive, Peer-led Initiative**

**NCT03207386**

**August 19, 2021**

## Data Analyses

All analyses were estimated in Stata 15. In all analyses, we used multiple imputation (MI; 20 imputed datasets) to address attrition and other missing data (Lang & Little, 2018). To address *Aim 1a*, we conducted a series of logistic regression analyses, one for each of the dichotomous W3 outcomes (i.e., sexual perpetration, sexual victimization). Covariates were sex (1 = *male*), ethnicity (1 = *Hispanic/Latinx*), race (1 = *White*), sexual orientation (1 = *sexual minority*), age (higher = *older*), school (dummy coded with the largest school as the comparison group), and the W1 outcome score (as applicable to each model).

Data collection protocols allowed for analysis of the long-term impact of the large camp and short-term impact of the small camp. However, because large and small camp attendance (e.g., youth could attend both camps) may co-vary they were included in the same model. That is logistic regression models examined the effects of both large camp attendance (0 = *did not attend*; 1 = *attended*) and small camp attendance (0 = *did not attend*; 1 = *attended*) on each primary outcome included in the model.

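### Does the SAP need a multiplicity rule because Aim 1a produces four camp effects on primary outcomes?

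*SAP*

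**What the plan says.** The SAP, under Data Analyses, says for Aim 1a that "we conducted a series of logistic regression analyses, one for each of the dichotomous W3 outcomes (i.e., sexual perpetration, sexual victimization"). That is two models. The second paragraph then says that the "logistic regression models examined the effects of both large camp attendance" and small camp attendance "on each primary outcome included in the model". Each model therefore gives two coefficients of interest, and both outcomes have primary status with no order between them.

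The SAP also explains why the two camps share a model: "because large and small camp attendance (e.g., youth could attend both camps) may co-vary they were included in the same model". It describes what the data allow as "analysis of the long-term impact of the large camp and short-term impact of the small camp".

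Neither the SAP nor the Protocol states a significance level, sidedness, a family of tests, a testing order, an adjustment, or a rule for declaring success. Neither says that familywise control is deliberately not sought.

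**The concern.** Four effects on primary outcomes with no stated error policy look like four chances to claim a benefit. If a report singled out whichever of the four was significant, a reader who took it for the only test would give it too much weight.

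The choice of family could also change a reading. If the smallest of the four p-values were 0.02, Holm's first step would give 2 × 0.02 = 0.04 when the family is one camp's two outcomes, and 4 × 0.02 = 0.08 when it is all four. At 0.05, these fall on opposite sides of the line. The p-value is hypothetical, since the documents show no results.

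**Working it through.** The plan gives no error rate, so there is no figure of its own to reproduce.

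**Inputs from the SAP (Data Analyses).** Two outcomes and two camp terms per model: 2 × 2 = 4 effects.

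**Inputs that must be assumed.**
- Two-sided 0.05 per test, so 0.025 in the favourable direction.
- Correlation between the test statistics for the two outcomes: 0 to 0.9.
- Correlation between the two camp coefficients: −0.6 to +0.6.
- All four effects null, and each test holding its nominal level.
- Success means any significant favourable result in the family.

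**Independent tests.** P(at least one false benefit) = 1 − (1 − 0.025)^k.
- k = 1: 0.025.
- k = 2: 1 − 0.975² = 0.0494.
- k = 4: 1 − 0.975⁴ = 0.0963. The upper bound under any correlation is 4 × 0.025 = 0.10.

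**Correlated tests.** Two tests use the bivariate normal tail beyond 1.96. Four tests use 2,000,000 four-variate normal draws, with the correlation matrix formed as the Kronecker product of the outcome and camp-coefficient matrices.

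| Outcome correlation | Two tests (one camp) | Four tests, over camp-coefficient correlations |
|---|---|---|
| 0 to 0.8 | 4.9% down to 3.9% | 9.75% down to 6.7% |
| 0.9 | 3.5% | 6.05 to 7.0% |

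Relative to 2.5%, the ratios run from 0.0352/0.025 = 1.4 to 0.0494/0.025 = 2.0 for two tests, and from 0.0605/0.025 = 2.4 to 0.0975/0.025 = 3.9 for four.

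**Dependence on the assumed level.** For independent tests at two-sided 0.01, the figures are 1 − 0.995² = 1.0% and 1 − 0.995⁴ = 2.0%. At two-sided 0.10, they are 1 − 0.95² = 9.75% and 1 − 0.95⁴ = 18.5%. The four-test figure thus moves from 2.0% to 18.5% on a number the documents do not contain.

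**What does not change.** The error rate of each effect, read on its own question, stays at 2.5% whatever the family. The expected number of false benefits among the four is 4 × 0.025 = 0.1 whatever the correlation. The inflation belongs to the statement that at least one of the four worked, and the SAP makes no such statement.

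**Cost of adjusting.** Take a test with 80% power at two-sided 0.05.
- Holm's first step over four tests (0.0125): Φ(1.960 + 0.842 − 2.498) = Φ(0.304) = 0.62.
- Holm's first step over two tests (0.025): Φ(1.960 + 0.842 − 2.241) = Φ(0.561) = 0.71.

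Power rises again at later steps. The gain, with all effects null, is that false benefit falls to 1.9 to 2.5% in the four-test family, or 2.0 to 2.5% in each per-camp family. Applying the per-camp version in both camps leaves 3.6 to 4.9% across the four.

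**The case for a change.** The strongest case for a change is that the gap survives the reading kindest to the plan. Even if each camp is its own question, each still has two primary outcomes, so the chance of a false benefit is still 1.4 to 2.0 times that of one test. A plan that names no success rule leaves readers free to supply the loosest one. The remedy looks cheap: adjusted p-values come from the four existing ones, with no new data or models.

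Part of this stands. The omission is real and is not explained by redaction or by how the PDF was read. A reader of the results will want the significance level and will want to see all four effects.

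The step from there to a required adjustment does not stand, for four reasons.
- The percentages would be the same for any study with two outcomes and two exposures. They describe a decision rule added from outside, not an error in this plan.
- The text does not settle the family. The SAP separates the "long-term impact of the large camp and short-term impact of the small camp" and joins the camps in one model because attendance may overlap, not because they form one joint hypothesis. Perpetration and victimization are also distinct outcomes. Requiring significance under both families would let the four-test family decide, since Holm over two of the four is never stricter. That family is no better supported by the text than the per-camp one, and it costs more power.
- The SAP is written in the past tense. A family chosen after the analyses lacks the protection of one chosen in advance.
- The comparison is by attendance with covariate adjustment, and neither document describes randomisation. If attendance is confounded, the 2.5% starting point fails and Holm does not repair it. A label of robust to multiplicity could then reassure more than it should.

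**Conclusion.** No change to the plan follows. Aim 1a does yield four camp effects without a stated error policy. Under the assumptions listed, at least one false benefit would occur with probability of about 3.5 to 4.9% per camp and 6 to 10% across the four, against 2.5% for one test. Those figures depend on an assumed 0.05 level, assumed correlations, valid tests, a global null and an any-success rule that is not in the SAP. They cover Aim 1a only; the label suggests other aims that the documents do not describe.

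What is left is a reporting detail that analysts fill as a matter of course: giving the level used and showing all four effects with confidence intervals and unadjusted p-values. With those in view, a reader who prefers a family of two or four can apply Holm directly. Whether to adjust separate questions in a non-randomised comparison is a fair trade-off on which statisticians differ, and the documents show no rule that gives a wrong result. Confounding by attendance is a separate matter that this point neither measures nor resolves.

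### Each W3 model adjusts only for its own W1 violence score and leaves out the other, already held, in an attended versus not-attended comparison: a minor, conditional and cheaply checked source of bias

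*SAP*

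**What the plan says.** Under Data Analyses (Aim 1a) the SAP states that "we conducted a series of logistic regression analyses, one for each of the dichotomous W3 outcomes (i.e., sexual perpetration, sexual victimization". The covariates are sex, ethnicity, race, sexual orientation, age, school dummies "and the W1 outcome score (as applicable to each model". That last item is singular and tied to the model, so the natural reading is that each model carries the baseline of its own outcome and nothing else on prior violence. No sentence puts both W1 scores in either model.

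The exposures are attendance at the large camp and at the small camp, each coded 0/1. They are modelled together: "because large and small camp attendance (e.g., youth could attend both camps) may co-vary they were included in the same model". The SAP describes the purpose in causal terms: "logistic regression models examined the effects of both large camp attendance".

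Neither document says how students came to attend a camp, and neither describes assignment, matching, weighting or a propensity score. Imputation has a different purpose: "we used multiple imputation (MI; 20 imputed datasets) to address attrition and other missing data". The Protocol dates the first survey to October to December 2017. Neither document dates either camp.

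**The concern.** When exposure is attendance and no assignment is described, the covariate list does all the work of making attenders and non-attenders comparable. The SAP already treats prior violence as worth adjusting for, but uses only half of what it holds. Each W1 score must have been collected, because each is the baseline covariate of one of the two models, yet neither enters the other model.

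Suppose students with W1 victimization were more (or less) likely to attend, and W1 victimization also predicted W3 perpetration after W1 perpetration and the listed covariates were allowed for. The perpetration model would then attribute part of that difference to the camps. The same holds with the roles reversed. At stake is whether either camp odds ratio is shifted away from its true value by something the sponsor could have adjusted for with data in hand.

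**Working it through.** **1. Covariates against outcomes.** There are two outcomes and two W1 violence scores, with one score per model. So 2 − 1 = 1 held score is left out of each model.

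**2. No plan figure to reproduce.** The documents give no outcome rate, attendance rate, target effect or power. The size of any bias can only be illustrated, and every input in step 3 is an assumption.

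**3. Inputs.**
- Assumed W1 prevalence is 15% for perpetration and 25% for victimization, with OR 4 between them.
- Each camp is attended by 20%. The camp-to-camp OR is 1 or 3.
- W3 risk is 8% with neither score. The own W1 score predicts W3 with OR 4; the other W1 score does so with OR 1.5, 2 or 4.
- The score-to-attendance OR (the link) is equal for both scores and both camps. The true camp OR is 1.
- Sample size comes from the Protocol: 2,232 at W1. The lower end uses the lowest retention in "retention from W1 ranged from 58.3% to 85.6% across waves": 0.583 × 2,232 = 1,301. W3-specific retention is not given.
- Demographics, school and multiple imputation are not modelled.

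**4. One case by hand** (perpetration model, link 1.5, omitted score to W3 OR 2, camps otherwise independent).
- Victimization prevalence is 20.5% without W1 perpetration and 50.7% with it (0.85 × 0.205 + 0.15 × 0.507 = 0.25; OR 4).
- No W1 perpetration: W3 risk is 0.080 without and 0.148 with W1 victimization. The share with W1 victimization is 26.2% in attenders and 19.1% in non-attenders. Risks are 0.080 + 0.068 × 0.262 = 0.0979 and 0.080 + 0.068 × 0.191 = 0.0930, so the OR is 1.057.
- W1 perpetration: W3 risk is 0.258 or 0.410 and the shares are 58.0% and 47.9%. Risks are 0.3463 and 0.3310, so the OR is 1.071.
- The logistic model with both camps and the own score gives a camp OR of 1.062, although the true OR is 1.
- At n = 2,232 the standard error of the log OR is 0.157. Bias/SE = ln(1.062)/0.157 = 0.38. The two-sided 5% false-positive rate is 1 − Φ(1.96 − 0.38) + Φ(−1.96 − 0.38) = 6.7%.

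**5. The grid.** Exact-probability logistic fits over both outcome models, both camps and both camp-to-camp values. OR ranges are for a null camp effect with the own score only; the false-positive rate is the maximum over n = 1,301 to 2,232.

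| Omitted score to W3 | Link 1.2 | Link 1.5 | Link 2 |
|---|---|---|---|
| OR 1.5 | 1.010 to 1.015; 5.1% | 1.022 to 1.036; 5.5% | 1.039 to 1.063; 6.6% |
| OR 2 | 1.017 to 1.027; 5.3% | 1.039 to 1.063; 6.7% | 1.070 to 1.111; 10.3% |
| OR 4 | 1.036 to 1.057; 6.6% | 1.083 to 1.132; 13.6% | 1.148 to 1.238; 31.7% |

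Inverse links of 1/1.2 to 1/1.5 give 0.95 to 0.99 for W3 OR 1.5 to 2, and as low as 0.89 for W3 OR 4.

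**6. Null checks.** With link OR 1, or with omitted score to W3 OR 1, the camp OR is 1.000. With both W1 scores in the model it is 1.000 in every case. Adding the score widens the camp standard error by about 1% to 6% for omitted score to W3 ORs of 2 to 4, and by less in most cases at OR 1.5.

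**The case against.** The plan does not contradict itself. Adjusting an outcome for its own baseline, demographics and school is a conventional specification. Both links that the bias needs are assumed, and both must hold after own baseline, sex, sexual orientation, age and school are allowed for. A similar argument could be made for any other variable collected at W1. This stands, and it limits the point to a conditional risk.

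The larger figures come from one corner of the grid. An OR of 1.24 and a false-positive rate of 31.7% need a link of 2 and an omitted score that predicts W3 as strongly as the outcome's own baseline (OR 4 each). A student with both scores would then also have 2 × 2 = 4 times the attendance odds. Nothing in the documents supports that. For links of 1.2 to 1.5 the bias stays below 0.9 standard errors throughout. The real models also add demographic and school covariates and use imputation; these would generally widen standard errors, and the covariates could absorb part of the bias. This stands too.

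The point also assumes that W1 preceded both camps. Using W1 as baseline makes that likely, but no camp date confirms it. Finally, an unchanged odds ratio after the refit would not show that attendance is unconfounded.

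What the objection does not remove is the omission itself. The left-out variable is the baseline of the companion primary outcome, it is already in the dataset, and no reason is given for excluding it.

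**Conclusion.** The point holds as a minor, cheap improvement. Each W3 model omits a held baseline violence score in a comparison whose only described protection against confounding is its covariates. If that score precedes the camps and relates to both attendance and the outcome given the listed covariates, both camp odds ratios in that model are biased by an unknown amount in an unknown direction. On the assumed inputs the bias is probably small: up to about 6% on the odds ratio for moderate links, and up to 13% when the omitted score is as predictive as the own baseline.

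A reader might infer that the reported camp odds ratios are wrong, or that students selected themselves into the camps. The documents support neither. They report no predictor of attendance and no association between the two scores, and they are silent on how attendance came about. Nor should the figures for a link of 2 be headlined, since they rest on the strongest assumptions in the grid.

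**What to change.** Refit both W3 models with W1 perpetration and W1 victimization both as covariates, and make sure that both scores are in the imputation model, whose variables the SAP does not list. Because the SAP reports analyses already carried out, present the refit beside the stated models as a labelled sensitivity analysis and say whether the camp odds ratios move. State that W1 preceded both camps, or say where it did not. Describe the camp coefficients as adjusted associations, since unmeasured selection into attendance remains either way.

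The cost is one extra covariate and one re-run per outcome on existing data, a camp standard error about 1% to 6% wider on the assumed inputs, one more set of results, and a wording change. No new data are needed.

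### Does putting both camps in one Aim 1a model, with no separate large-camp model, misstate the large camp's long-term impact?

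*SAP*

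**What the plan says.** The Data Analyses section of the SAP describes "a series of logistic regression analyses, one for each of the dichotomous W3 outcomes". There are two outcomes, perpetration and victimization, so there are two models.

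The second paragraph gives the target: "Data collection protocols allowed for analysis of the long-term impact of the large camp and short-term impact of the small camp". It then gives the modelling decision and the reason for it: "However, because large and small camp attendance (e.g., youth could attend both camps) may co-vary they were included in the same model". The next sentence restates the model, beginning "That is logistic regression models examined the effects of both large camp attendance", and codes each camp as 0 or 1.

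The adjustment set is sex, ethnicity, race, sexual orientation and age, and it ends with "school (dummy coded with the largest school as the comparison group), and the W1 outcome score (as applicable to each model". The SAP mentions no interaction term and no model with only one camp. The Protocol does not mention the camps.

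**The concern.** A reader may take the long-term impact of the large camp to mean everything that attending it changed, including any later decision to attend the small camp. Long-term and short-term effects measured at the same wave suggest, without saying so, that the large camp came first. If it did, and if it fed the small camp, then small-camp attendance lies on the path from large camp to outcome, and adjusting for it removes that part of the effect. An unmeasured cause of both small-camp attendance and the outcome could also introduce collider bias.

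At stake is how a null result is read. An OR near 1 would mean no association with small-camp attendance held fixed, yet it might be reported as no long-term impact at all.

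**Working it through.** The documents state no OR, outcome rate, attendance rate or camp date, so there is no figure of the plan's to reproduce. The check has two parts.

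**1. What the text commits to.** Two outcomes with one model each give one large-camp coefficient per outcome, adjusted for the small camp. This is explicit and comes with a reason. Any coefficient in a multivariable model is conditional on the other terms; the SAP does not label the camp coefficients as conditional on school or W1 score either. The SAP does not define the large camp's impact as including effects through the small camp. Its stated purpose is to separate two exposures that can occur in the same student.

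**2. How far the two estimates could differ.** All rates and effects here are assumptions.

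*By hand.* Take a risk of 10% without the small camp, a small-camp OR of 0.60 and a conditional large-camp OR of 1.00.
- Odds with the small camp: (0.10/0.90) × 0.60 = 0.0667, a risk of 0.0625.
- If 10% of large-camp non-attenders go to the small camp, their risk is 0.9 × 0.10 + 0.1 × 0.0625 = 0.09625.
- If 30% of large-camp attenders go, their risk is 0.7 × 0.10 + 0.3 × 0.0625 = 0.08875.
- OR without the small-camp term: (0.08875/0.91125) / (0.09625/0.90375) = 0.0974/0.1065 = 0.914.
- If 10% go in both groups, the risks are equal and the OR is 1.00, as in the joint model.

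*Over a grid.* Exact population calculation with 20% large-camp attendance, 10% or 20% baseline small-camp attendance, 15% outcome, small-camp OR 0.60 or 0.80, and no direct large-camp effect. The multiplier is the factor by which the large camp raises the odds of small-camp attendance. The unmeasured trait is binary, coded ±1, with log-odds 0.7 or 1.0 on attendance and on outcome.

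| Setting | True total OR | Large-only OR | Joint OR |
|---|---|---|---|
| No trait, multiplier 1 | 1.00 | 1.00 | 1.00 |
| No trait, multiplier 1.5 to 2 | 0.94 to 0.99 | same as total | 1.00 |
| No trait, multiplier 3 to 10 | 0.77 to 0.97 | same as total | 1.00 |
| Shared protective trait, multiplier 1 to 10 | 0.815 to 1.00 | 0.33 to 0.63 | 0.43 to 0.81 |
| Shared risk-raising trait, multiplier 1 to 10 | 0.79 to 1.00 | 1.12 to 1.86 | 1.18 to 1.85 |

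The high multipliers are extreme. At 10, small-camp attendance goes from 10% to 1.111/2.111 = 53%, or from 20% to 2.5/3.5 = 71%.

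*Collider bias.* With the trait acting on the small camp only and multipliers 1.5 to 2, the joint OR is 1.02 to 1.09 (protective) or 0.92 to 0.98 (risk-raising). But log-odds of 0.7 or 1.0 on a ±1 trait mean an OR between trait groups of exp(1.4) = 4.1 or exp(2.0) = 7.4. With log-odds 0.2 or 0.35 (between-group OR about 1.5 or 2.0), the joint OR is 0.985 to 1.015, a bias of at most about 1.5%. The grid also omits the SAP's covariates; the W1 outcome score could absorb part of such a trait.

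*Which estimate is closer to the true total OR, on the log scale.* With no shared trait and a multiplier above 1, large-only is closer in 80 of 80 settings. With a shared trait, joint is closer in 40 of 40 protective and 27 of 40 risk-raising settings, so 67 of 80.

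*Sampling error.* The Protocol reports "Most students ($n = 2,232$; 83.6%) with guardian permission took the survey". If those 2,232 students were the analysis set, with 20% attendance and 15% outcome, SE = √(1/(2232 × 0.2 × 0.8 × 0.15 × 0.85)) = √(1/45.5) = 0.148, and exp(±1.96 × 0.148) = 0.75 to 1.34. This ignores covariates and imputation. The two estimates share data, so their difference varies less than this.

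**The case for a change.** The strongest case for the concern is that disclosing a model does not tell the reader what its coefficient means. If the large camp did steer students to the small camp, the joint OR would miss part of what most people would call the large camp's impact, and in every such setting without a shared trait the large-only OR is nearer the total effect. A sentence, a cross-tabulation of attendance and two extra models would cost little.

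The logic is sound, and a report would be clearer if it gave the order of the camps and the overlap in attendance. But that is missing detail, and a reader of the SAP can see that each camp is adjusted for the other.

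The extra model is harder to defend. Where a shared tendency to attend camps underlies the overlap, which is one natural reading of the SAP's remark on co-variation, the large-only estimate is usually the worse one. With a shared protective trait and multiplier 1, the truth is 1.00, large-only gives 0.40 to 0.63 and joint gives 0.43 to 0.65: the two nearly agree and both are wrong. So agreement would not reassure, and a difference could reflect mediation, collider bias or shared propensity. The SAP is also written after the fact ("All analyses were estimated in Stata 15"), so a second large-camp OR per outcome would be post hoc and open to selective reading.

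**Conclusion.** The concern does not stand. The SAP specifies a legitimate joint model, says that it does so and says why. The supposed defect needs two things that neither document supplies: a target defined as the large camp's total effect, and evidence that the large camp changed small-camp attendance. Without that influence and without a shared trait, the two estimates coincide.

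Under the assumed rates, an influence of 1.5 to 2 on the odds scale and no trait would separate them by about 1% to 6%, against a rough interval of 0.75 to 1.34. Larger gaps need a stronger influence of one camp on the other or a strong unmeasured trait. If that trait is shared by both camps, the large-only model is usually further from the truth. The actual size and direction cannot be found from the documents. Self-selected attendance could bias either estimate, and choosing between the two models does not cure that.
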